#### Waiver of assent with a substitute of an information sheet

Our study requests a waiver of assent with a substitute of an information sheet (**as suggested by the IRB**) to be provided to enrolled minors. The IRB may waive the requirement for the investigator to obtain a signed consent form for some or all subjects if it finds (based on 45 CFR 46.117(c)(1)):

- Principal risks are those associated with a breach of confidentiality concerning the subject's participation in the research
  - *This study collects behavioral information about the participant, such as sexual behaviors. This is sensitive information. The principal risk to the participant is confidentiality.*
- Consent document is the only record linking the subject with the research.
  - *This study does NOT collect dates of birth or HIV status. This study does collect medical record numbers and phone numbers. The only record linking the subject's name with the research would be her consent form. (We have omitted the release of medical information form to comply with this term). All patients will receive a unique identifier. Only at the time of follow-up will her name as read from the medical record; however, researchers will be blinded to any behavioral information already provided in the study by that participant.*

In addition, we believe that our study presents **MINIMAL risk**. Participants will not be exposed to the possibility of harm -- physical, psychological, social, legal, or other -- as a consequence of participation as a human subject in this research activity. This study should not increase the probability or magnitude of risks ordinarily encountered in daily life. We believe this to be true for the following reasons:

- The sexual health information we will send via mobile phone is similar to the sexual health education received in schools, which is approved by state and federal initiatives.
- The principal threats to adolescent health and well-being are social and behavioral: personal behavior and the behavior of peers. Behavioral research includes intervention programs to reduce harmful behaviors and increase protective behaviors as well as projects designed to improve understanding of the factors influencing adolescent behavior. Behavioral research generally presents little risk to the individual adolescent. Research on the prevention of HIV and teen pregnancy has resulted in more effective prevention programs to reduce sexual risk behavior.
- The primary risks to the adolescent participant from behavioral research, particularly survey research, are potential embarrassment and disclosure of sensitive information to others. This is true for survey research involving adults as well. However, disclosure resulting from survey research is a rare phenomenon.

*Additional reasons that support our request for a waiver of assent with a substitute of an information sheet AND a waiver of a parental consent are the following:*

- F. The definition of children in the federal regulations recognizes the legal status of mature and emancipated minors under state law and the ability of adolescents to consent for specific health services. These state minor consent laws implicitly recognize that under certain circumstances minors are capable of making independent judgments and that this emerging decision-making capacity should be respected. Parental permission is not required under the federal regulations, where adolescents do not fit the regulatory definition of children.
- G. Patients who are younger than 18 years old and present to the ED for a reproductive health care concern can legally provide their own consent. New York Public Health Law (Title 1, #2305 (2)) states that a person under the age of 21 years may receive reproductive health care without the consent or knowledge of parents or guardians of said person, when said person has been infected or exposed to a sexually transmitted disease.
- H. New York Consolidated Law, Social Service Law 350(e). Family planning services and supplies shall be offered and promptly furnished to eligible persons of childbearing age, including children who can be considered sexually active, who desire such services and supplies, in accordance with the regulations of the department.
- I. Using the US federal definition of children, teenagers presenting for reproductive complaints are not considered children and are considered adults for research purposes. The federal Title X legislation requires that confidential services be available to adolescents in Title X-funded family planning clinics, such as the Columbia family planning clinic, and the US Supreme Court has extended privacy rights in matters related to the use of contraception to minors.
- J. Under the federal regulations governing research, the IRB may waive the requirement for parental permission for research involving children (including minor adolescents) if parental permission is deemed not reasonable or ethically problematic. The National Commission noted that IRBs may determine that parental permission may not be appropriate, for example, regarding health care for contraception. Adolescents' rights to both clinical care and research may be compromised if parental permission is required for research participation. We strongly believe that adolescent confidentiality is RISKED in this study if there is parental consent.

#### Study Procedures: (different than Part 1)

After a patient provides informed consent, participants will complete a baseline questionnaire (new version attached as a Document, which is a shorter version of Part 1 baseline questionnaire).

Participants will then be block-randomized into one of two arms, Text Messaging (TM) or Standard Referral (SR). Participants will receive a \$10 gift card.

After randomization, participants in the TM arm will receive the texting intervention. The server will store all libraries of branched-logic messages and responses. All ingoing and outgoing texts will be time-stamped, recorded, and accessible to investigators.

Patients randomized to the SR arm will receive a welcome text message and then standard medical care as decided by their emergency medicine physician.

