## Study Procedures

Eligible enrolled patients will either text message in the ED will confirm intervention receipt (manual enrollment) or will text RipRoad for enrollment (technological enrollment). This will ensure texting capabilities.

10 participants will receive the 2 month intervention as a beta test. They will receive weekly follow-up calls to qualitatively assess real-life occurrences, such as current sexual activity, change in pregnancy intentions, and perspectives of the messages. Questions will include, “*What about the program is least or most engaging?*” and “*How have your contraceptive choices change because of the texts?*”.

Other probes may include questions about message frequency and time of day. Texts will then be refined and finalized. 40 participants will receive the complete intervention to assess feasibility and acceptability, and potential effectiveness. These participants will not be assessed weekly but rather 3 months after enrollment (week 12).

We expect that approximately 10 of the 50 participants will have technological issues with their phones such as phone disconnections. That is why we have a target accrual of 50 but an actual accrual of 40.

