## Part 2: The pilot randomized control trial

Strategy: We will conduct a pilot RCT of 250 adolescent females at high risk of unintended pregnancy to receive either the 10-week texting program, [name], or standard discharge instructions. *We hypothesize that the texting program will be feasible, acceptable, and increase contraceptive initiation rates (our primary outcome).*

Setting: We will recruit patients from the pediatric ED at New York-Presbyterian Children's Hospital, which cares for over 50,000 patients per year. Patients are predominantly Hispanic, insured, and of low socioeconomic status.

Subjects: The eligibility criteria is the same as Study Part #1. Inclusion: (1) age 14-19 years and (2) sexually active with males in the past 3 months. Exclusion: (1) currently using any "effective" form of contraception (as defined by the World Health Organization and includes the Shot, intrauterine device, ring, implantable device, Patch, birth control pills, or sterilization), (2) do not own a mobile phone with texting, (3) are pregnant, (4) are too ill for participation per the attending physician, (5) are cognitively impaired, (6) do not live locally within the 5 boroughs, Westchester, Rockland, Nassau or Suffolk counties, (7) do not speak English or (8) want to "become pregnant in the next year."

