Data for secondary outcomes will also be collected via phone follow up and EMR review during month 3 and interactive text messaging at weeks 3 and 6. A baseline survey will collect information regarding demographics, reproductive and sexual history, prior medical care, and pregnancy intentions. Questions were adapted from the Youth Risk Behavioral Survey, National Survey of Family Growth, and written *de novo*.

Analysis: We will analyze both an intention-to-treat (ITT) population and per-protocol population. The ITT population will include all enrolled and randomized patients. The per-protocol population will only include participants who completed follow-up and, for those in the intervention group, excludes those who received none of the text messages. Acceptability and Feasibility: We will summarize outcomes related to feasibility and acceptability using standard descriptive statistics and conduct exploratory bivariable analyses to identify characteristics of participants who appear more likely to opt out of the study (in order to develop further retention strategies). Potential efficacy: We will calculate the absolute risk difference (ARD) between groups with exact test-based 95% confidence intervals. For the ITT analysis, the outcome for those lost to follow-up will be imputed conservatively as *contraception not initiated*. We will use the chi-square test to determine the potential effect of the intervention on contraception initiation. We will conduct exploratory multivariable logistic regression analyses to test if age group (older (18-19 years) versus younger (17 and younger)), ethnicity, race, prior family planning clinic visits, having a primary care provider, prior pregnancy, and prior use of contraceptives, potentially confound or modify the effect of texting on contraception initiation. We will also examine texting response rates over time and how this relates to contraception initiation. We will also measure changes in contraception knowledge and decisional conflict based on proportions.

Sample size: Using prior ED studies, we expect to enroll approximately 250 patients over 2 years. Accounting for a 20% lost to follow up rate, this would enable us to detect a 17% absolute increase in contraception initiation

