(assuming 17% in SR arm, based on prior data) with 80% power ( $p=0.05$ , two sided). We readily understand that the effect size is likely not to be this large. As this is a pilot trial (Phase II), our goal is to gather the preliminary data needed for a definitive, multi-center RCT grant application (Phase III). We also plan to enroll equal proportions of younger (aged 14-17) and older (aged 18-19) adolescents to verify our prior findings that age modifies the effect of the intervention, with younger teens more often initiating contraceptives than older teens.

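### Part 2 describes no working-phone check before randomisation, so a text-arm participant whose number fails at enrolment would stay in the ITT comparison

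*Combined protocol and SAP*

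**What the plan says.** **Part 2 sequence.** The section Study Procedures (different than Part 1) lists consent, a baseline questionnaire, block randomisation and then texts. For the TM arm: "After randomization, participants in the TM arm will receive the texting intervention". SR participants get a welcome text, also after allocation. No test text is described.

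**Part 2 phone criterion.** Under Subjects, patients are excluded if they "2) do not own a mobile phone with texting" (exclusion 2). Under Recruitment, the treating provider is asked to confirm eligibility.

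**Part 1.** Enrolled patients exchange a text in the ED, by manual or technological enrolment: "This will ensure texting capabilities". The same section adds: "We expect that approximately 10 of the 50 participants will have technological issues with their phones such as phone disconnections".

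**What carries over.** Part 2 labels Recruitment as the same as Part 1, and Sources of material as the same except where noted. Study Procedures is labelled as different.

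**After allocation.** Undelivered texts lead to an email asking for a new number (Sources of material). Bounce-backs are feasibility outcome (d), expected below 20% (Outcomes and Data Sources). The ITT set is everyone randomised, with loss to follow-up counted as not initiated. The per-protocol set needs completed follow-up and, in the TM arm only, drops those who received no texts.

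**Sample size.** "we expect to enroll approximately 250 patients over 2 years"; after 20% loss, "this would enable us to detect a 17% absolute increase in contraception initiation" ("assuming 17% in SR arm, based on prior data").

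**The concern.** Owning a texting phone does not show that the recorded number can receive the programme. A mistyped number or an inactive line would pass exclusion (2) and be randomised. In the TM arm, unless the number is later repaired, that participant gets no programme, is expected to initiate contraception at the SR rate, and remains in the ITT set.

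The remedies in the plan all act after allocation. The per-protocol exclusion for non-receipt has no SR counterpart, so it selects on one side. A check before allocation falls equally on both arms and introduces no such selection.

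Three further things are at stake:
- The pilot is meant to supply data for a definitive trial, so a diluted estimate would carry forward.
- Without a count at enrolment, outcome (d) cannot separate phones that never worked from later disconnections.
- A wrong number could send sexual-health texts to someone else. The plan names confidentiality as the principal risk and treats its loss as an adverse event.

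**Working it through.** **Inputs.** From the Sample size paragraph: SR rate 17%, difference 17 points (so TM 34%), total 250, loss 20%, two-sided 0.05, power 80%. The allocation ratio is not stated, so 1:1 is assumed. Evaluable: 250 × 0.8 = 200, or 100 per arm. The share f of TM participants whose phone fails at enrolment and is not repaired is not in the documents, so 2%, 5% and 10% are assumed values.

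**Step 1: the plan's own figure.** Two-proportion normal approximation with pooled variance under the null, where p̄ is the mean of p1 and p2:

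z = [√n (p2 − p1) − 1.96 √(2p̄(1 − p̄))] / √(p1(1 − p1) + p2(1 − p2))

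With n = 100, p1 = 0.17, p2 = 0.34 and p̄ = 0.255:

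z = (1.700 − 1.96 × 0.6164) / 0.6046 = 0.814, so power = 79.2%.

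The stated 80% is reproduced. With unpooled variance the requirement is 99.3, so 100 per arm, and 200 / 0.8 = 250 exactly.

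**Step 2: dilution.** If non-receivers initiate at the SR rate, the TM rate is 0.17 + (1 − f) × 0.17 and the difference is 17 × (1 − f) points. For f = 5%: TM rate 0.3315, difference 16.15 points, z = (1.615 − 1.201) / 0.602 = 0.687, power 75.4%.

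**Step 3: the full ITT set.** Here n = 125 per arm and the 20% lost count as not initiated, so both rates are multiplied by 0.8. At f = 0 the rates are 13.6% and 27.2%.

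| f (assumed) | TM rate | Difference (points) | Power, 100 per arm | Total N for 80% power (pooled, /0.8) | Power, full ITT, 125 per arm |
|---|---|---|---|---|---|
| 0 | 34.0% | 17.0 | 79.2% | 258 | 76.4% |
| 2% | 33.7% | 16.7 | 77.7% | 265 | 74.9% |
| 5% | 33.2% | 16.2 | 75.4% | 280 | 72.5% |
| 10% | 32.3% | 15.3 | 71.2% | 310 | 68.4% |

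**Step 4: overlap with planned loss.** The table assumes that non-receivers are spread evenly over followed and lost participants. If instead every non-receiver is among the 20% already expected to be lost, the full-ITT rates stay at 13.6% and 27.2%, and power stays at 76.4% whatever f is, up to 20%. The true cost lies between no further loss and the values in the table.

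**The case against.** The case for leaving the text alone has real force.

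- **Silence is not removal.** Part 2's Study Procedures are brief, the messages are in attachments not available here, and the website link given on enrolment has no stated channel. A reader might infer that Part 2 deliberately dropped the check. The documents show only that none is described. The heading that marks these procedures as different does mean that the Part 1 step cannot be assumed.
- **The criterion is checked.** A reader might infer that nobody verifies the phone criterion. It is ownership, and the provider confirms eligibility. What is missing is a functional check.
- **Neither quoted rate measures failure at enrolment.** A reader might take the 10 of 50 in Part 1 as a 20% ceiling for f, which would give 13.6 points and 62% power. That figure was expected with the ED text exchange in place, and its example is disconnection. The 70.9% delivery in the earlier pilot is per message over 3 months (1172/1654), not per participant on the first day. Part 2 itself attributes undelivered texts mostly to disconnected numbers, which a test in the ED would not prevent.
- **Safeguards exist.** The email request can repair a number, and outcomes also come from telephone follow-up, an emailed survey link and the medical record. A failed number therefore means neither certain non-receipt nor certain loss of outcome.
- **Randomising all phone owners is defensible in a feasibility pilot.** Non-receipt is part of the effect of offering the programme, and screening could flatter outcome (d). Part 1's exchange also applied to patients already enrolled, so using it as a gate to randomisation is a new step.

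These points limit the size and the wording. They do not remove the gap: every described remedy follows allocation, and one of them selects on one arm. Reporting test failures separately answers the worry about outcome (d).

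**Conclusion.** The point holds in a limited form. Part 2 describes no functional phone check before randomisation, and any TM participant with an unrepaired failing number moves the ITT difference toward zero. At 100 per arm the cost is about 1.5 points of power at f = 2% (79.2 − 77.7), 4 at 5% (79.2 − 75.4) and 8 at 10% (79.2 − 71.2), and less where these patients overlap with the planned 20% loss. This rests on 1:1 allocation, non-receivers initiating at the SR rate, and an f that the documents do not give. The low end is more plausible.

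A reader might go further and conclude that the ITT analysis or the sample size is wrong. Neither follows. Keeping everyone randomised is correct, the stated power reproduces, and 17 points is a detectable difference that the plan itself says is likely larger than the true effect. This is a modest, inexpensive improvement to the design.

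**What to change.** In Part 2 Study Procedures, between consent and randomisation, add a step of this kind:

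> Before randomisation, every consented patient completes one neutral test-text exchange with the study platform in the ED. If it fails, the number is checked, corrected and retested on the spot. Only patients who complete the exchange are randomised.

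Align exclusion (2) with this step. Report the number failing the test as a separate feasibility count beside outcome (d), so that the bounce-back figure is not flattered. If such a check is already done in practice, state that and when it takes place.

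The cost is one automated text per patient on a platform already in use; SR participants already receive a welcome text. A few phone owners will not be randomised, so the result applies to patients with reachable phones. Later disconnections are not prevented, so the email request for new numbers is still needed.

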### **Sources of material** (same as Part 1 except for when mentioned as unique to Part 2)

Similar to our prior texting trial (**IRB #AAAM3457**), we will collect data from the EMR, a baseline survey, telephone follow-up, and mobile platform provider.

- The EMR tracking board in the ED will be used by research coordinators and investigators to identify potentially eligible patients. The EMR will also be used to collect follow-up information. (See Documents)
- A baseline survey will collect information regarding
  - Demographics (such as age and grade in school),
  - Reproductive and sexual history (such as prior use of birth control methods, age at first intercourse, and number of sexual partners),
  - Prior medical care (such as last time to a primary care provider and history of contraceptive counseling by a provider),
  - Contraceptive knowledge,
  - Decisional conflict with choosing a contraceptive method,
  - Psychosocial mediators of behavior change (self-efficacy, self-esteem, social support)
  - and pregnancy intentions (such as wanting and timing of future pregnancies).

Questions for the survey were adapted from the Youth Risk Behavioral Survey, National Survey of Family Growth, The Fog Zone (Guttmacher validated survey set) and others written *de novo* based on investigator expertise. (See Documents)

- Telephone follow-up phone calls will be completed to determine outcomes, including contraceptive initiation. (See Documents)
- Two-way text messages will be delivered and received by RipRoad, a HIPAA-compliant mobile provider. This company has been used by Columbia University researchers in the past (see studies by [name]) and has a Business Agreement with Columbia.
- Upon enrollment into the study, participants will watch two short videos and receive a link to the website, [www.dr-erica.com](http://www.dr-erica.com).
  - The first video is a short explanation of our program which can be viewed at [www.dr-erica.com/introductory.video](http://www.dr-erica.com/introductory.video).
  - The second video a video about birth control options which can be viewed at <https://vimeo.com/271757026>.
  - In our prior qualitative interviews, we learned that adolescents receive their health information from unreliable sources, especially on the Internet. We created [www.dr-erica.com](http://www.dr-erica.com) as a one-stop website that contains reliable, medically accurate links to websites such as StayTeen.org and Bedsider.org. Topics include birth control options, local clinics, testimonials, and an introduction to who Dr.Erica is. Many of the links we sent to teens in our texts are on this site. This site contains NO Columbia identifiers, collects NO patient identifiers, and is approved by Columbia University Information Technology.

- (NEW TO THIS MODIFICATION): We will be asking for email addresses for the following two reasons:
  - Disconnected phone numbers: Adolescents often change phone numbers. If RipRoad reports that a phone number has “undelivered” texts, that is usually due to a disconnected phone number. We will email that participant (using the email template attached in Documents) to ask for an updated phone number.
  - Follow up: If a participant does not complete the follow up survey (sent via text as a link), she will be sent an email with the follow-up survey link (using the email template attached in Documents).
- All text messages are attached under Documents.
- Based on preliminary feedback from Study Part 1, we found that many adolescent text questions into the program such as “Where can I get birth control pills?”. Because this program is automated, when questions are received, we send an error message that reads, “Sorry, we do not understand that. If you are answering a question, please reread & try again. If you have general questions, check out [www.dr-erica.com](http://www.dr-erica.com).” Therefore, these questions are never answered by the program. As a solution to this, we have built in “[name] Hours.” This will work in the following manner:
  - Any incoming response (text into the program by a participant) that is 4 or more words will trigger two events:
    - A response text to the participant which reads as follows: “Sorry, I don’t understand your text. But we can answer your questions LIVE during our [name] Hours. You can text privately with a confidential health educator who can answer all your questions! [name] Hours are from 7-8pm. I’ll have her text you this week and let you both connect. In the meanwhile, check out dr-erica.com.”
    - An email to the study PI: All texts received into the RipRoad system will trigger an immediate email to the PI. This will alert to PI who will be texted during the [name] Hours.
  - [name] Hours: These will occur from 7-8:30pm. [name] (the PI and board-certified pediatrician and pediatric emergency provider) will manage the text message interactions. She will follow the [name] Hours Handbook (attached as a document) and dispense no personal medical advice. The email interaction will begin as follows:

1. Introduction Example: “Hi [nickname]! Welcome to [name] office hours.”
2. Warm welcome Example: “We will be open for the next hour and able to answer your questions. I am trained health professional and what you say here is private and confidential.”
3. Clarifying questions Example: “I see you asked [name] a question. You asked [insert question here]. I think I can help you answer that.”

- [name] will answer this question using the [name] Hours Handbook. These questions and answers are evidence-based and many borrowed from a Planned Parenthood Program that provides live chat opportunities for women across the US. This program has been in existence for several years and has provided medical information to thousands of women across the USA.
- If a participant poses a question outside the scope of this handbook, such as medical advice (which we define as anything outside the scope of our guidebook), she will receive the following text:

- “I am sorry but that is outside the scope of what I can answer by text message. I suggest you talk to your medical provider or call the Family Planning Clinic for an appointment. You can also check out dr-erica.com for more information.”

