### Outcomes and Data Sources:

Feasibility will be operationalized as the following dependent variables: (a) rate of refusal to participate (*expected <20%*), (b) opt outs (texted to stop receiving messages; *expected <5%*), (c) loss to follow up (*expected <20%*), (d) technological failures (frequency and proportion of text message “bounce backs”; *expected <20%*), (e) response to texting interactivity, as an indicator of engagement (*expected >80%*), and (f) time to reply to texting interactivity (*expected <15 sec*). Data for these outcomes will come directly from our mobile platform provider.

Acceptability will be based on participant feedback. We expect that participants will “*like*” messages (*>4* on a Likert scale) and find the intervention “*relatable*,” “*helpful*,” and “*engaging*,” when asked open-ended questions about the intervention. These outcomes will be determined during month 3, 2 weeks after the 10-week intervention, via phone follow up and web-based survey sent via text message link.

Efficacy The primary outcome is effective contraception initiation, defined as (1) patient self-reports initiation at phone follow up or via text or (2) there is electronic medical review (EMR) documentation of initiation. If there is a discrepancy between self-report and EMR documentation (e.g. received prescription but never started pills), we will prioritize self-report. We define “*contraception not initiated*” if noted by self-report to not have initiated or if lost to follow up and no evidence of initiation in EMR.

Similar to our cohort study, our second primary outcome is decisional conflict. This measures a participant’s level of commitment to choosing a birth control method and has been used in other contraceptive studies and is a validated scale. We are using the low literacy version to meet the needs of our adolescent population.

We will also conduct exploratory analyses to identify characteristics of participants who appear more likely to opt out of the study (allowing us to develop further retention strategies). Finally, we will examine texting response rates over time and how this relates to contraception initiation.

Secondary outcomes include follow-up to reproductive care clinics, pregnancy rates, an increase in condom use, talking to an adult about birth control, and psychosocial mediators of behavior change.

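### The plan asks for a new phone number only when texts bounce, so texts and the month-3 survey link can reach someone else, and number updates would mostly reach the texting arm

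*Combined protocol and SAP*

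**What the plan says.** The email provisions are in Part 2, Sources of material. The first reason for collecting addresses is that "Adolescents often change phone numbers". When the texting provider reports undelivered texts, the protocol says "that is usually due to a disconnected phone number. We will email that participant", and the purpose is "to ask for an updated phone number". No other event leads to that request. The second reason is non-completion of the follow-up survey, in which case "she will be sent an email with the follow-up survey link". That step re-sends the link and does not ask about the number.

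The month-3 measures come "via phone follow up and web-based survey sent via text message link" (Outcomes and Data Sources). For contraception initiation, self-report by phone or text counts, and it takes precedence over the EMR where the two disagree. Participants who cannot be reached and have nothing in the EMR are counted as not having initiated.

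The same Sources of material section describes the live texting hours. An incoming text of four or more words brings an automatic reply saying the educator will "have her text you this week and let you both connect". The example opening then has three steps: a greeting by nickname, a welcome with a statement that the exchange is private, and "You asked [insert question here]. I think I can help you answer that".

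The waiver section for Part 2 states: "The principal risk to the participant is confidentiality". Data and Safety Monitoring makes any loss of confidentiality an adverse event.

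**The concern.** A bounce detects a dead number. It does not detect a live number that has passed to someone else, or a phone that is shared or handed on. Having recognised that numbers change, the plan checks only for the kind of change that announces itself.

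Two things are at stake. The first is confidentiality. The texts concern contraception and sexual health in girls as young as 14, enrolled without parental permission precisely to protect their privacy. The privacy reassurance in Data and follow-up rests on locked phones and on parents not reading messages, and does not deal with a changed number. The monitoring plan responds to a breach after it has happened. Its question about feeling threatened or being hurt because of the texts is asked in the follow-up phone survey, which may use the same number.

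The second is even-handed follow-up. The texting arm receives ten weeks of messages, each of which can bounce and prompt an update. The referral arm is described as receiving one welcome text and then usual care. Updated numbers would therefore accumulate mainly in the texting arm, while an unreachable participant without EMR evidence is scored as a failure in either arm.

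**Working it through.** **1. Which events lead to a check of the number**

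| Event | What the plan does | Number rechecked? |
|---|---|---|
| Number disconnected, text bounces | Email asking for a new number | Yes |
| Number now belongs to someone else, text delivered | Nothing stated | No |
| Phone shared or handed on, text delivered | Nothing stated | No |
| Survey not completed | Survey link emailed | No |
| Survey completed by another person | Nothing stated; the emailed link is not sent | No |

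Part 1 has a text exchange in the ED, but that is a single check of texting capability at enrolment. The Part 2 Study Procedures do not repeat it.

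**2. When the trigger can operate, by arm**

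- Texting arm: throughout the 10-week programme, then again when the survey link is sent at month 3 (2 weeks later).
- Referral arm, from Study Procedures: at the welcome text, then not until the survey link. A disconnection in between is first seen when the survey link itself bounces.
- One uncertainty: Outcomes and Data Sources also mentions interactive texting at weeks 3 and 6 for secondary outcomes, without naming an arm. If the referral arm receives those texts, it has two intermediate points at which a bounce could be seen. That is still far fewer than in the texting arm.

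**3. The live session**

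A session follows only from a text sent by the same phone. The new holder of a reassigned number would mostly see their own question repeated. What remains is a phone that is shared, or changes hands, between the question and the reply, a wait of up to a week. The example opening has no pause for her answer before the question is repeated.

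**4. Size**

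The documents give no rate at which numbers pass to another holder without bouncing. The prior pilot's delivery figure (1172/1654 = 70.9%) shows that phone contact is unstable here, but it counts undelivered texts, not texts delivered to the wrong person. By arithmetic alone, each 1% of numbers in other hands is 0.01 × 250 = 2.5 survey links.

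For the primary outcome, start from the plan's own power figure. Inputs: 17% versus 34%, about 250 enrolled, 20% lost, two-sided 0.05, and 1:1 allocation (assumed; the ratio is not stated). Evaluable per arm: 250 × 0.8 / 2 = 100.

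Power = Φ{[d√n − 1.96√(2p̄(1−p̄))] / √(p₁(1−p₁) + p₂(1−p₂))}, with d = 0.17, p̄ = 0.255, n = 100

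= Φ{(1.700 − 1.208) / 0.605} = Φ(0.81) = 79.2%, which reproduces the stated 80%.

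Now suppose, purely as an assumption, that a share m of true initiators in both arms is recorded as not initiated because someone else answered. The difference becomes 17 × (1 − m) points:

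| m (assumed) | Difference, points | Power at 100 per arm |
|---|---|---|
| 0 | 17.0 | 79.2% |
| 2% | 16.7 | 78.1% |
| 5% | 16.2 | 76.4% |
| 10% | 15.3 | 73.3% |

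Unequal reach acts differently. In the intention-to-treat analysis with 125 per arm, each initiator missed in the referral arm but not in the texting arm widens the observed difference by 1/125 = 0.8 points, in favour of the intervention.

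**The case against.** The case against is substantial, and much of it stands.

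- **The outcome has back-ups.** If a stranger ignores the link, the participant is emailed it, and telephone follow-up and EMR review remain. A wrong outcome needs someone else to complete a contraception survey as if they were the participant. This stands. What it leaves open is that a completed survey stops the emailed link, and that self-report outranks the EMR.
- **Key documents are not in view.** The opening lines are given as examples, and the live hours follow a Handbook that is an attachment, as are the message texts, email templates and follow-up survey. Any of them may already contain a confirmation step. This stands; the point covers only what the protocol itself says.
- **The live session discloses little.** It starts from the same phone, the question would normally still be in the message thread, and the participant is told when to expect contact. This largely stands and limits the point to a shared or handed-over phone.

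A reader might be tempted to go further in two ways. One is to infer that a stranger with a reassigned number would be told the participant's question; the trigger for the session rules that out in the main. The other is to take the expected texting response above 80% as a sign that the silent remainder have lost their phones. Silence is not evidence of a changed number, and non-response need not fall in the same people.

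**Conclusion.** The gap is real on the face of the protocol. The plan recognises that numbers change, but rechecks them only on a bounce. Programme texts and the survey link can therefore reach another person unnoticed, and number updates would mainly reach the texting arm. Confidentiality is the main ground.

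The statistical effect cannot be sized from the documents. Under an assumed 2% to 10% of initiators misrecorded in both arms, the loss is 0.3 to 1.7 points of difference and about 1 to 6 points of power, assuming 1:1 allocation. The unequal-reach effect is 0.8 points per participant, of unknown frequency. It also depends on Study Procedures being complete as to what the referral arm is sent. None of this supports a claim that the primary result would be seriously biased. The change is worth making because the risk is one the plan itself ranks first and the remedy is small.

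**What to change.** 1. **Sources of material, email addresses.** Shortly before month 3, and before the survey link is texted, send the existing number-update email to all participants in both arms on the same schedule. Keep the bounce trigger as it is. State in Study Procedures whether the week 3 and week 6 interactive texts go to the referral arm.
2. **Sources of material, live texting hours.** After the welcome, wait for a reply that she is there and can text privately, and only then repeat her question. Do not rely on the nickname: the greeting has already given it away. If the Handbook already has such a pause, cite it in the protocol.

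Do not make a nickname-and-age match a condition for counting the survey as self-report. With birthdays spread evenly, about 12/52 = 23% of genuine participants (roughly 58 of 250) would turn a year older within 12 weeks and fail a literal match to baseline age. Any of them not then reached by phone and without EMR evidence would be scored as not initiated.

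The cost is one extra email per participant, to addresses already collected, and a slightly slower start to live sessions. The email protects the survey link; it does nothing for programme texts sent before it.
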